3.7.1.3 In-game questionnaire

The in-game questionnaire occurs after each level achieved by the player. It asks two questions on a seven point scale: 1) does the subject enjoy the game; 2) how difficult did the subject find the game? In addition, the subject is able to mention other aspects considering their play experience. The questions (in Finnish) can be found in Appendix 7 - Data collected in the study.

3.7.1.4 In-game behaviour

The investigational device feels and displays as a video-game to the subject. Subject navigates in an interacting 3D environment by using keyboard and mouse. The subject's interactions with the game made with keyboard and mouse are stored in game logs. Subject experiences 28 tutorialized game levels that include performing various cognitive tasks that target specific cognitive functions. Purpose of any given game round is to conquer all the monuments. This includes defeating the opposing forces, solving tasks and overcoming challenges.

Performance values from these cognitive tasks, like reaction time, correct answer and execution time, are stored in the game logs and are used in evaluating gameplay performance values. These performance values are evaluated after each game and used for adapting the task difficulty individually to achieve the training effect.

The game includes a narrative and the subject receives feedback from their game progression to support learning. Subject has an avatar that yields magical, non-violent abilities. These include skills that can be used e.g. to alter temporal structure globally or locally, teleport to a location, cast a damaging beam of light or freeze enemies. Use of abilities is stored in game logs. Avatar has also the ability to command up to three friendly allies with defensive and offensive capabilities. Commands assigned to friendly allies are stored in game logs. These performance values are evaluated after each game and used for adapting the task difficulty.

3.7.1.5 Clinical interview

The clinical interview is conducted prior to the intervention. The aim of the interview is to evaluate whether the subject meets the inclusion and exclusion criteria. The clinical interview is described in 3.6.5.2, and in Appendix 5 - Clinical subject coordinator phone call. The clinical interview is conducted remotely by a trained, clinical professional.

3.7.1.6 Experiential interview

Qualitative research is ever more frequently used in randomised controlled trial (RCT) studies to explore the feasibility and acceptability of the intervention (Cooper et al., 2014). Using video games as a therapeutic modality is most likely a new concept for the majority of our subjects, and it is vital to gain insight into how they perceive the intervention.

To complement the questionnaire and in-game data gathering, we conduct interviews to the subjects who indicate their interest in participating in an interview. The aim is to interview approximately 20 subjects.

The interview is conducted online and it takes 1-1.5h. The aim of the interview is to understand 1) how the subjects view playing video games as a treatment modality; 2) explore how the player experiences playing Meliora, and 3) explore possible effects the game may have had.

For details on the interview protocol, see Appendix 8 (Appendix 8 - Interview study).

3.7.2 Data-analysis-inclusion criteria and handling of missing data

To be included in the analysis of the primary hypothesis, the subject has to

- Have played the game version A or B at least 24 hours (50% of the recommended 48 hour game time) during the 12 weeks.
- The subjects must have answered all of the PHQ-9 items on both T0 and T2 or T3.

Handling of missing data:

- Primary endpoint evaluation will be based on the comparison of scores acquired ~~at~~ between T0 and T3.
- When the subject has played the MEL-T01 or MEL-S01 for 24 hours, but the T3 PHQ-9 score is missing, we will use the T2 PHQ-9 score.
- If the subject has accumulated ≥ 24 hours of intervention use and then ceased the use, we will use the first PHQ-9 score after the cessation of use.
- Subjects that do not meet these criteria are excluded from the analysis.
- In regards to our secondary hypotheses, missing data are handled similarly.

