The subjects ($N = 800$) volunteering to participate in this investigation are diagnosed with MDD and have an on-going mental health treatment contact with a mental health professional. The subjects are recruited through Helsinki and Uudenmaan sairaanhoitopiiri (HUS) psychiatry and Varsinais-Suomen sairaanhoitopiiri (VSSHP) psychiatry as well as online.

The subjects are randomised into three arms with equal probabilities in blocks of six consecutive subjects. Subjects in the MEL-T01 and MEL-S01 arms are engaged in the intervention for 12 weeks while those in the TAU arm are on a follow-up period during these 12 weeks.

After this 12-week period, the subjects in MEL-T01 and MEL-S01 arms enter a 12-week follow-up period and the subjects in TAU arm engage with either the MEL-T01 or MEL-S01 intervention (randomised at T0 with equal probability) for 12 weeks (See Table 1 below).

The subjects are recommended to play the investigational-device game for a total of 48 hours during the 12 weeks of active intervention with a recommended weekly dose of 4 hours. A minimum of 24 hours is needed for inclusion to hypothesis testing. The subjects are limited to a daily maximum of 1.5 hours of game time.

Prior to the intervention, a clinical interview (MINI) is performed via phone to confirm the subject's MDD diagnosis. The subjects' mental health symptoms and well-being are evaluated through online questionnaires five times: before subjects are randomised into one of the three groups (T0), and then 4 (T1), 8 (T2), 12 (T3), and 24 (T4) weeks after the study has begun.

Subject population:**Criteria for inclusion:**

Eligible subjects must fulfil all of the following criteria:

1. Between 18-65 year-old
2. Suffering from major depressive disorder
3. Have an ongoing mental health treatment contact to basic healthcare, specialised healthcare, student healthcare or occupational healthcare
4. Has sufficient eyesight with or without prescription
5. Has a Windows computer with internet connection and mouse
6. Has email and phone number

Criteria for exclusion:

Subjects who fulfil any of the following criteria are excluded from the study:

1. They have threat of self-harm
2. They have addiction to digital games
3. They have psychotic disorders
4. They are pregnant or breastfeeding
5. They have impaired ability in decision making
6. They are prisoner or forensic subject
7. They have neurological disorders such as epilepsy or brain injury

Safety assessments:

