3.6.4.3 Investigation data exempt from blinding

For the purpose of **subject monitoring**, the CSCs and excluding all other investigators, will have access to the gaming-time and questionnaire-completion-status data of individual identifiable subjects. This information will be available to the CSCs for AE report, email, or

phone call interactions with the subjects so that the CSCs are able to make informed inferences, e.g., about the subject's study compliance. Notably, the CSCs will also have access to the suicidality-related questionnaire responses for subject monitoring as specified in [3.6.3.5](#). The CSCs remain blinded to all other investigation data, and especially the data about the study arm, game performance, and all other questionnaire replies of the subjects.

For the purpose of **study monitoring**, the investigators, excluding the CSCs, will have access to the gaming-time, questionnaire-completion-status, and study-arm data of individual but unidentifiable subjects. These data will enable the assessment of whether the criteria for the interim analysis or study completion are met.

- These data are needed because the interim analysis (see [3.7.5](#)) is triggered when each arm has 33 subjects that have completed the intervention (specifically, the 12 first weeks, which are follow-up for the TAU arm) and meet the inclusion criterion (see [3.7.2](#)) to data analysis.
- Conversely, termination of the investigation (see [3.7.4.2](#)) will be triggered when each arm has 133 subjects that have completed both the intervention and the follow-up period and meet the inclusion criterion (see [3.7.2](#)) to data analysis.

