3.7.4 Power and sample size

3.7.4.1 Power analysis

A power analysis was conducted to determine appropriate sample size for the study to detect a statistical difference between change scores for the primary hypothesis in a two tailed, repeated measures t-test. Assuming that our samples are independent and identically distributed with normal distribution (see [3.7.3](#)), we analyse the required sample size as follows:

- We conduct sample size analysis using G*Power 3.1.9.7
- We use a two-tailed t-test.
- Cohen (1988) suggests a small effect size is 0.20 and medium effect size is 0.50. As a point of comparison, a meta-analysis of internet-based treatments for adult depression have reached an average effect size of 0.41 (Anderson & Cuijpers, 2009). Meanwhile, Motter et al. (2016) found in their meta-analysis that computerised cognitive training had an effect size of 0.43 on depression symptom severity. Thus, we use an effect size $d = 0.40$.
- We use an alpha error probability of 0.0167 that corresponds to an alpha level of 0.05 with Bonferroni correction for the three primary endpoint tests.
- We use power of 0.80
- We allocate subjects equally to the three arms, leading to allocation ratio of 1:1:1

This leads to a total sample size of 133 per arm and with three arms this equals 399 subjects, which we round to **400 subjects** that we aim to have in T3.

Karyotaki et al. (2015) explored the dropout in self-guided web-based interventions for depression using different psychotherapeutic approaches. While their approach is based on psychotherapies, and ours on cognitive training, the medium of training is the same

(web-based), the intervention is self-guided, and they target people with depression. Karyotaki et al. found that in 10 RCTs 59% of the subjects dropped out before completing half the treatment modules.

Meanwhile, Torous et al. (2020) explored dropout rates for app interventions for depression. Considering publication bias, they found a dropout rate of 47.8%.

Considering the above, we assume a dropout rate of 50%. Thus, we aim to recruit up to 400 subjects / 0.50 = 800 subjects to begin the study.

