3.10.1 Subjects deviations or violations

The majority of human made deviations are mitigated because the majority of the intervention is digital: answering questionnaires as well as playing the game. Wherever possible, we have mitigated the possibility for the subject to deviate from the CIP.

Before the subject is included in the research, they complete the signup process (see 3.7.1.1), first set of clinical questionnaires (see 3.7.1.2), and their MDD diagnosis is confirmed through clinical interview (see 3.7.1.5). Only then the subject is randomised to MEL-T01, MEL-S01, or TAU group, and they are given access to the intervention (for groups MEL-T01 and MEL-S01). Thus we mitigate the risk of the subject not meeting the inclusion/exclusion criteria.

When the subject arrives at T1, T2, T3, and T4, they are emailed the instructions to complete clinical questionnaires. In addition, the reminder to complete the questionnaires is shown to the MEL-T01 and MEL-S01 group in the game, and they are not able to make progress until they have completed the questionnaires. The questionnaires are filled online. If the subject doesn't fill the questionnaires in 7 days from the onset of T1, T2, T3, or T4, they are followed up with a phone call by the CSC.

The subject is recommended to play the game for 48 hours during the 12 week play period. To be included in the sample we require 24 hours of gameplay. When the subject is contacted by the CSC, the CSC has access to the subject total game time and number of weeks played (but they do not know the subject group). If the subject total game time divided by the number of weeks played is less than 2 (the minimum required), the CSC kindly discusses the topic with the subject encouraging them towards reaching 24-48 hours of playing time during the 12 week play period.

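### The only primary analysis set keeps game-arm subjects by hours played after randomisation, so both comparisons with TAU lose the protection of randomisation

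*Combined protocol and SAP*

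**What the plan says.** Section 3.7.2 sets two conditions for entering the analysis of the primary hypothesis. The first is "Have played the game version A or B at least 24 hours", which is half of the recommended 48, within the 12 weeks. The second is "The subjects must have answered all of the PHQ-9 items on both T0 and T2 or T3". It then states "Subjects that do not meet these criteria are excluded from the analysis", and handles missing data for the secondary hypotheses in the same way.

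The synopsis (3.1.6) repeats the rule: "A minimum of 24 hours is needed for inclusion to hypothesis testing". So does 3.10.1: "To be included in the sample we require 24 hours of gameplay". None of the three places exempts TAU or gives it a criterion of its own.

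Tables 1 and 6 give TAU no game access before T3. Yet 3.6.4.3, 3.7.4.2 and 3.7.5 count TAU subjects who meet 3.7.2 towards the triggers of 33 and 133 per arm. For the interim trigger, 3.6.4.3 describes the first 12 weeks as ones "which are follow-up for the TAU arm".

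Section 3.7.2 also ties outcome substitution to play. A T2 score replaces a missing T3 score in a subject who reached 24 hours. For a subject who reached 24 hours and then stopped, the first score after stopping is used.

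No intention-to-treat, all-randomised or sensitivity analysis appears anywhere in the documents.

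**The concern.** Hours played are observed after randomisation and depend on the subject's own behaviour. People who persist for 24 hours may differ from those who stop in motivation, severity and likely course. If the game arms keep only persisters while TAU keeps everyone with PHQ-9 data, the groups compared are no longer those that randomisation made alike. Any prognostic difference is then counted as device effect in two of the three primary contrasts.

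The plan's secondary hypotheses (3.5) expect game time to correlate positively with PHQ-9 reduction. Such a correlation could be causal, prognostic or both, and a primary analysis that selects on game time cannot separate these.

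The same set triggers the interim analysis, on which the benefit and harm rules (3.7.5.1, 3.7.5.2) are applied, and it closes recruitment (3.7.4.2). The bias could therefore reach decisions about stopping as well as the final test.

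**Working it through.** **1. The plan's own sample size.** Inputs from 3.7.4.1: two-tailed t-test, alpha 0.0167, power 0.80, d = 0.40, allocation 1:1:1, 50% dropout. With the non-central t and 133 per arm, the non-centrality is 0.40 × √(133/2) = 3.26 and power is 0.803. So 133 reproduces. Then 3 × 133 = 399, rounded to 400; 400/0.50 = 800; and 800/3 ≈ 267 randomised per arm. The arithmetic is sound. The 133 are, however, subjects selected after randomisation.

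**2. Who can meet the rule.** If the 12 weeks are T0 to T3, TAU subjects cannot log any play. The interim trigger nevertheless needs 33 TAU subjects who qualify at the end of a period that is follow-up for them. The workable reading is that TAU qualifies on the PHQ-9 condition alone.

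**3. Bias with no device effect.** Assumptions, none of them in the documents: a standard normal propensity to play, correlated r with standardised PHQ-9 improvement; the fraction q with the highest propensity passes; TAU is unfiltered. The shift in the game-arm mean is r × φ(z)/q, where z = Φ⁻¹(1 − q). The multiplier φ(z)/q is 1.159 for q = 0.3, 0.798 for q = 0.5 and 0.497 for q = 0.7. With 133 against 133, the non-centrality is shift × √(133/2) = shift × 8.155, and the one-sided 0.0167 critical value is 2.138 (264 df). Each cell gives the shift in SD, then the false-positive rate per TAU contrast.

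| Share passing | r = 0.1 | r = 0.2 | r = 0.3 |
|---|---|---|---|
| 30% | 0.116; 12% | 0.232; 40% | 0.348; 76% |
| 50% | 0.080; 7% | 0.160; 20% | 0.239; 43% |
| 70% | 0.050; 4% | 0.099; 9% | 0.149; 18% |

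Allowing for the smaller variance in the filtered arm moves these by at most about two points. A simulation of 5,000 trials with half passing gave 1.7%, 7.2%, 19.9% and 43.1% for r = 0, 0.1, 0.2 and 0.3. If TAU supplied 213 subjects (an assumed 80% of 267), the 50% row becomes 8%, 25% and 51%.

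**4. The opposite sign.** With r = −0.2 and half passing, the shift is −0.160. A true effect of 0.40 would then appear as 0.240, and one-sided power at 133 per arm falls from 87% to 43%. At the interim look (33 per arm, one-sided 0.0125) with no device effect, the non-centrality towards harm is 0.160 × √(33/2) = 0.65. The chance of meeting the harm criterion in one contrast rises from 1.25% to about 5%.

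**5. MEL-T01 against MEL-S01.** The bias is the difference between two shifts. It is zero if both games retain the same share and kind of subject. If 50% passed in one arm and 70% in the other at r = 0.2, it would be 0.160 − 0.099 = 0.061 SD.

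**6. Power if all randomised subjects are analysed.** Suppose half of a game arm plays under 24 hours and keeps a fraction k of an effect of 0.40. The overall d against TAU is 0.40 × (0.5 + 0.5k): 0.20 for k = 0, 0.30 for k = 0.5, 0.40 for k = 1. Two-sided 0.0167 t-test:

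| T3 data per arm | d = 0.40 | d = 0.30 | d = 0.20 |
|---|---|---|---|
| 267 (all) | 99% | 86% | 46% |
| 213 (assumed 80%) | 96% | 76% | 37% |
| 133 (about 50%) | 80% | 52% | 22% |

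**The case against.** The 24-hour rule is deliberate and openly stated. Section 3.2.10.6 argues from the training literature that short exposure gives unreliable findings, and gives 24 to 72 hours as the range for a reliable test of efficacy. A question about efficacy in those who receive an adequate dose is legitimate. That supports a per-protocol analysis beside the main one. It does not support using it as the sole basis for superiority to TAU.

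Four stronger readings are tempting, and the documents do not bear them out.

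- *No TAU subject can ever be analysed.* This holds only if the play condition is applied literally to TAU over T0 to T3. Section 3.6.4.3 shows that TAU subjects are expected to qualify after a follow-up period, so this is a drafting gap. One could also count TAU play after T3. That fits the interim trigger badly, and it would select TAU subjects on behaviour later than their T3 outcome.
- *The plan itself expects to discard half of each game arm.* Section 3.7.4.1 says "Considering the above, we assume a dropout rate of 50" (per cent). It applies that figure to all three arms and aims for 400 subjects at T3. One cited source (59% stopping before half the modules) resembles the 24-hour rule; the other (47.8%) is described only as dropout. The share failing 24 hours is not stated.
- *The bias favours the device.* No figure in the documents fixes the sign or size of r.
- *MEL-T01 against MEL-S01 is compromised to the same degree.* Both arms face the same filter, subjects are blinded between the games (3.6.4.1), and the games are designed to be similarly engaging (3.6.2). Exposure there is possible but not shown.

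**Conclusion.** The concern stands for both TAU contrasts. On the only workable reading of 3.7.2, the sole primary analysis compares self-selected players with an unfiltered control arm, so a significant result could not be attributed to the device with the assurance of a randomised comparison. The criterion also needs rewording because it does not fit TAU as written. The contrast between the two games is exposed conditionally.

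The magnitude is illustrative. Across pass rates of 30% to 70% and r of 0.1 to 0.3, the false-positive rate per TAU contrast runs from 4% to 76% against a nominal 1.67%. These figures rest on the normal-propensity model, an unfiltered TAU arm and 133 per group. A negative r reverses the direction. This should be corrected before the data are analysed.

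**What to change.** In 3.7.2, with matching edits in 3.1.6 and 3.10.1:

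- Define the primary analysis, and that of the secondary outcomes, as all randomised subjects in the arm assigned. Use all observed T0 to T3 scores in the mixed model already planned in 3.7.3, whatever the hours played.
- Remove from that analysis the T2 and first-score-after-cessation substitutions, which depend on play.
- Keep the 24-hour set as a labelled supplementary analysis, citing the dose rationale in 3.2.10.6.
- Limit any complier-type estimate that uses randomisation as the instrument to the two game-against-TAU contrasts. State its assumption of no effect below 24 hours. The graded dose hypothesis in 3.5 makes that assumption doubtful, and the method does not carry over simply to a contrast in which both arms play.
- In 3.6.4.3, 3.7.4.2 and 3.7.5, define the 33 and 133 triggers by PHQ-9 availability in all three arms, and plan recruitment to the randomised total.

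Data collection need not change: 3.10.1 already provides emailed questionnaires at T1 to T4 with a telephone follow-up of non-responders. These contacts matter most for subjects who stop playing, since the in-game reminder will not reach them.

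The cost is more than wording. Non-players dilute the effect, so 3.7.4.1 must restate power under declared assumptions on dilution and T3 completeness (step 6 of the working). With complete data from 266 per arm, 80% power needs an overall d of about 0.28, which means that subjects below 24 hours keep about 41% of the effect: (0.281/0.40 − 0.5)/0.5 = 0.41. The power table counts only subjects with T3 data; earlier scores in the mixed model may recover part of the loss.

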3.7.3 Hypothesis tests and multiple comparisons

Primary and secondary objectives in this clinical study are to demonstrate a statistical difference on outcome measure mean change scores between the following groups:

1. MEL-T01 and MEL-S01
2. MEL-T01 and TAU
3. MEL-S01 and TAU

We will first assess whether we use a parametric or non-parametric test.

- Using the Shapiro-Wilk test we explore if MEL-T01, MEL-S01, and TAU model residuals are normally distributed regarding PHQ-9.
- Using Levene's test we test whether the variance of MEL-T01, MEL-S01 and TAU model residuals are equal regarding PHQ-9.
- If both tests are $p > 0.05$, we will use a repeated measures Linear Mixed Model; If either test is $p < 0.05$, we will use a repeated measures Linear Mixed Model with robust standard errors.
- For primary endpoint evaluation (PHQ-9), we will conduct a one-tailed test for the arm pairs MEL-T01-vs.-MEL-S01, MEL-T01-vs.-TAU, and MEL-S01-vs.-TAU. We

are using a significance level of 0.05. Using Holm-Bonferroni correction, we find the multiple-comparison corrected $p = 0.05/3 = 0.0167$.

Change scores are defined as the scores obtained between the pre-intervention (T0) assessment and the during/post-intervention assessments. The general formulation of the null and alternative hypotheses are

$$H_0: \mu_x = \mu_y$$

$$H_1: \mu_x \neq \mu_y$$

where H_0 is the null hypothesis, H_1 is the alternative hypothesis and $x, y \in \{A, B, TAU\}$, $x \neq y$.

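### Section 3.7.2 restricts the primary analysis to subjects with a PHQ-9 at T2 or T3, discarding earlier leavers' T0 and T1 scores that the planned mixed model could use

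*Combined protocol and SAP*

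**What the plan says.** Section 3.7.2 sets two conditions for the primary analysis. One is playing time: "Have played the game version A or B at least 24 hours". The other is outcome response: "The subjects must have answered all of the PHQ-9 items on both T0 and T2 or T3". It then states: "Subjects that do not meet these criteria are excluded from the analysis". The response condition names no arm. TAU subjects cannot play before T3, so if the hours condition is read as meant for the game arms, the response condition is the only one that filters TAU.

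There are two replacement rules. For subjects with 24 hours of play "but the T3 PHQ-9 score is missing, we will use the T2 PHQ-9 score", and for those who stop after reaching 24 hours "we will use the first PHQ-9 score after the cessation of use". For the other endpoints: "In regards to our secondary hypotheses, missing data are handled similarly".

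Section 3.7.3 names the model: "we will use a repeated measures Linear Mixed Model", with robust standard errors if an assumption check fails. Under 3.7.1.2, the T0 questionnaires must be completed before randomisation, and the PHQ-9 is repeated at T1, T2, T3 and T4 in all arms. Section 3.7.4.1 plans for heavy loss: "Considering the above, we assume a dropout rate of 50" per cent. The visible text contains no analysis of all randomised subjects, no imputation and no missing-data sensitivity analysis.

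**The concern.** A likelihood-based mixed model uses partial records and is valid when missingness depends only on observed scores. That is the main reason to choose it over a comparison of completers. Here the response condition is applied before the model is fitted, so a subject with T0 and T1 but nothing later contributes nothing. The primary hypotheses compare arms as assigned on change to T3; the analysis compares only those still answering at week 8 or 12.

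The plan gives reasons to expect different leaving by arm. Game-arm subjects can tire of the game, and 3.10.1 blocks their in-game progress until questionnaires are completed. Under 3.6.3.4 a subject may be discontinued for a device-related adverse event, which cannot arise in TAU before T3. TAU subjects have nothing to stop and receive the game after T3, which is a reason to stay. If early response drives leaving in one arm more than another, the retained sets stop being comparable, and the T1 scores that could correct for it have been dropped.

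This is separate from the 24-hour rule: removing that rule alone would leave the response condition in place.

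**Working it through.** **1. The plan's own figures.** Inputs from 3.7.4.1: d = 0.40, two-sided alpha 0.0167, power 0.80, two-sample t-test. The noncentral t gives 133 per arm (power 0.803). 3 × 133 = 399, rounded to 400; 400 / 0.50 = 800. The stated sizes reproduce. On these figures 800 − 399 = 401 subjects, about 50%, fall outside the primary analysis. The documents do not divide them between too little play and no T2/T3 score.

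**2. Who the response rule removes.** Assume the 50% loss is spread evenly over T0–T1, T1–T2 and T2–T3, at 20.6% per interval.
- Still answering at T3: 0.794³ = 0.50.
- Without T2, so removed by the rule: 1 − 0.794² = 0.37.
- Of these, without T1 either: 0.206, about 21% of the arm.
- With T0 and T1 only: 0.794 × 0.206 = 0.16. These are the subjects whose usable follow-up is discarded.

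Subjects lost after T2 are kept, so this is a T2/T3-responder set rather than a strict complete-case set.

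**3. Effect on a contrast.** Assumptions, none of them in the documents: changes at T1, T2 and T3 normal with SD 1; correlations 0.7 (T1–T2), 0.5 (T1–T3), 0.7 (T2–T3); true effects 0.2, 0.3, 0.4; loss before T1 ignorable; later leaving logistic in the last observed change; hours rule and T2-for-T3 replacement switched off; 1,000,000 subjects per arm. The T3 means are maximum-likelihood estimates for monotone missingness, computed in the T2-observed set and again in everyone with T1. Odds ratios are for leaving, per SD of poorer response.

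| Loss per interval | Odds ratio, game vs TAU | T2/T3-responder set | T1-only subjects kept |
|---|---|---|---|
| 20.6% each | 1.5 vs 1.25 | 0.42 (about +5%) | 0.40 |
| 20.6% each | 1.5 vs 1 | 0.44 (about +10%) | 0.40 |
| 20.6% each | 2 vs 1 | 0.47 (about +17%) | 0.40 |
| 20.6% each | 2 vs 2 | 0.40 (about 0) | 0.40 |
| 20.6% each | 1/1.5 vs 1 (better responders leave the game) | 0.36 (about −10%) | 0.40 |
| 20/30/10% | 1.5 vs 1 | 0.46 (about +15%) | 0.40 |
| 10/40/7% | 2 vs 1 | 0.53 (about +31%) | 0.40 |

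For scale, the standard error of a contrast at 133 per arm is √(2/133) = 0.123. The even-loss upward shifts of 0.02 to 0.07 are therefore about 0.02/0.123 = 0.16 to 0.07/0.123 = 0.57 of a standard error.

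**4. A second set-up: no true effect, unequal loss.** Assumptions: PHQ-9 SD 5, equal correlation 0.5 or 0.7, 267 randomised per arm, leaving after T1 with log-odds rising 0.5 to 1.0 per SD of T1 worsening in both arms, one-sided t-test on change at 0.0167.
- 50% leave the game arm and 20% leave TAU: bias 0.22 to 0.59 PHQ-9 points in favour of the game; type I error 0.064 to 0.157.
- 30% and 10% leave: bias 0.15 to 0.41 points; type I error 0.038 to 0.102.
- Leaving unrelated to the T1 change, or loss equal in both arms: bias about zero.
- A likelihood estimate that keeps T0 and T1: bias within 0.02 points throughout.

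So an unequal loss rate is enough to cause bias when leaving follows early response, even if the dependence itself is the same in both arms.

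**The case against.** The strongest reply is that the rule's own effect, under the plan as it stands, may be modest in the game arms. At the recommended 4 hours a week a subject has 4 × 4 = 16 hours by T1, so most game-arm subjects who leave between T1 and T2 would fail the 24-hour condition anyway. The simulations switch that condition off. This stands: the share due to the response rule alone cannot be computed from the documents.

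Retention efforts also count. All arms receive emails, a call after seven days without a response (3.10.1) and scheduled calls (3.14.1), and compensation requires all questionnaires (3.15.1). These reduce non-response but do not remove it, and the plan still budgets for 50% loss.

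Three stronger readings are tempting and are not supported.
- A reader might infer that the analysis is valid only if T2/T3 response is unrelated to early response. That is true of arm means, but the hypotheses concern contrasts, and selection that acts equally in the arms leaves these about unbiased.
- A reader might apply the whole 50% to this rule. If lost and kept subjects differ by 0.08 SD in one arm only, 50% gives 0.50 × 0.08 = 0.04 (10% of 0.40). Under even loss the rule removes 37%, giving 0.37 × 0.08 = 0.03 (about 7%).
- A reader might infer that the bias always favours the game. The direction depends on who leaves, which the documents do not say.

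Finally, recovery of 0.40 by the fuller model is built into the assumption that leaving depends on observed scores. It would not correct for leaving driven by unobserved worsening.

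**Conclusion.** The concern holds in a limited form. As written, 3.7.2 fits the mixed model to a T2/T3-responder set and discards the T0 and T1 scores of earlier leavers in all arms. Bias in the contrasts needs leaving before T2 to select on early response differently by arm. Under the stated assumptions a true 0.40 becomes about 0.42 to 0.47 in one direction or about 0.36 in the other with even loss, and can reach about 0.53 with heavier loss between T1 and T2. These sizes are illustrations: the documents give no within-subject correlations, no loss by arm and no loss by visit. The sample size is not in question, since 800 already allows for 50% loss. The point is worth correcting because expected loss is high, the T1 scores will be collected anyway, and no sensitivity analysis would reveal the problem.

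**What to change.** - **Primary analysis.** Replace the T2-or-T3 requirement with the 3.7.3 mixed model fitted to all randomised subjects with a T0 PHQ-9. Use every observed T1, T2 and T3 score, include arm-by-time terms, and take the T3 contrast as the primary estimate. This also settles two gaps in 3.7.2: a TAU subject with T2 but no T3 is admitted without a specified endpoint score, and the cessation rule can point to T1 (24 / 1.5 = 16 days of maximum play) while the response condition still requires T2 or T3.
- **All arms alike.** Lift the 24-hour condition from the primary analysis in the same amendment. Otherwise TAU leavers would return while game-arm leavers stayed excluded, which increases the asymmetry.
- **Triggers.** Recruitment closure (133 per arm, 3.7.4.2 and 3.6.4.3) and the interim analysis (33 per arm, 3.7.5) both refer to 3.7.2. Keep T2/T3 response as a separately named count for these, and state whether hours remain part of that count. If only T0 were required, closure could occur at about 399 enrolled, with no allowance for loss.
- **Sensitivity.** Add one analysis that shifts missing T3 scores in the game arms towards TAU.
- **Secondary scales.** Handle them the same way.

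The cost is rewording in 3.7.2 and in the trigger sections, plus some programming, with no new visits or patients. The drawback is more reliance on the missing-at-random assumption, which the sensitivity analysis tests.
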